10.2. Expected Disease Related Events

In this study population, with DR-TB and HIV, some participants may be critically ill and will have a complicated clinical course. Opportunistic infections and/or nosocomial infections are expected. Disease-related events may be frequent and include:

- Death which will always be reported as an SAE
- HIV-related opportunistic infections / illnesses
- Common ART side-effects e.g. anaemia, sleep disturbance, diarrhoea, mild renal dysfunction
- Hospitalisation due to respiratory symptoms or HIV related conditions

Expected disease-related events will be recorded in study CRFs but will not require reporting to regulatory authorities unless the severity of the event was considered to be unexpected.

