8. TREATMENT CONSIDERATIONS

8.1. Interruptions to treatment

The study treatment regimen may be interrupted at the discretion of the local PI for:

- A serious adverse event
- The investigator decides to withhold treatment in the interest of the safety and well-being of the participant
- Lack of effectiveness

If treatment is interrupted for a suspected serious drug reaction, attempts should be made to identify the drug concerned. After resolution of the suspected adverse reaction, treatment may be gradually re-introduced until the allocated regimen has been re-instituted.

In the case of the BPaL regimen, if treatment is interrupted for more than 35 consecutive days, the participant will be referred to the assigned expert TB clinical committee to decide on further management including need for change to a new individual regimen, based on clinical assessment and reason for interruption. Any missed doses should be made up at the end of the treatment to complete 24 weeks of therapy. Missed doses of linezolid alone due to adverse reactions are not to be made up at the end of treatment. Reasons for missing treatment must be identified and addressed early and noted in the participant's file for analysis for factors associated with (lack of) treatment success (33).

In the event that the local PI considers that treatment needs to be modified or changed, he or she should inform the coordinating centre by submission of an SAE form and discuss treatment plans with a member of the study medical monitoring team (MMT).

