10.3. Serious Adverse Event Reporting

An SAE or Serious Adverse Reaction (SAR) or Suspected Unexpected Serious Adverse Reaction (SUSAR) includes an experience where any AE, AR or UAR that at any dose:

- Results in death;
- Is life-threatening;
- Requires hospitalization or prolongation of existing hospitalization;
- Results in persistent or significant disability or incapacity; or is a medically significant/important event or reaction that may not be immediately life-threatening or result in death or hospitalization but may jeopardize the participant or may require intervention to prevent one of the other outcomes listed in the definition above.

All serious ADRs will be reported.

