Adverse Reactions*	Common: diarrhoea, nausea, vomiting, headache, transient increases in LFTs. Serious: myelosuppression (decreased level of platelets, white blood cells, and/or anaemia), optic and peripheral neuropathy (increased risk with prolonged treatment and may be irreversible) lactic acidosis (may present recurrent nausea or vomiting, unexplained acidosis, or a low bicarbonate level).
Contraindications	Hypersensitivity to oxazolidinones. Symptoms of neuropathy (pain, numbness, tingling or weakness in the extremities).
Drug Interactions*	Avoid concurrent use with serotonergic agents, such as monoamine oxidase inhibitors (MAOIs), selective serotonin reuptake inhibitors (e.g. fluoxetine, paroxetine), lithium, tricyclic antidepressants etc., as it may cause serious neurological reactions such as seizures and serotonin syndrome.
Guidance on monitoring	Monitor for peripheral neuropathy and optic neuritis (visual eye tests every two months or if symptoms develop, clinical examination for peripheral neuropathy monthly or if symptoms develop). Monitor a complete blood count weekly during the initial period, then monthly.
Moxifloxacin	
Activity against TB, Mechanism of action, and metabolism	Bactericidal: inhibits DNA gyrase
Dose	Adults: 400 mg daily (oral or IV)
Special Circumstances	Use in renal disease: Excretion unchanged during renal failure; no data on effect of dialysis. Use in hepatic disease: Rarely associated with hepatotoxicity; use with caution. No dose adjustment required for mild or moderate liver disease. Use during pregnancy/breastfeeding: Fluoroquinolones are generally avoided during pregnancy and breastfeeding due to observation of arthropathy in animal models. However, there are

	case reports of fluoroquinolones being used safely during pregnancy.
Adverse Reactions*	Common: Nausea, vomiting, diarrhoea, dizziness, headache, transient increases in LFTs. Serious: QTc prolongation (more common in hypokalaemia, predisposing cardiac conditions, or if combined with other QTc prolonging drugs), arthralgia, tendon inflammation and/or rupture, hepatotoxicity, hypo/hyperglycaemia.
Contraindications	Fluoroquinolone intolerance, prolonged QTc (>500ms). Fluoroquinolones may lower seizure threshold, so use with caution in participants with CNS disorders.
Drug Interactions*	Caution if used alongside other drugs known to prolong QTc.

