13. HUMAN PARTICIPANT PROTECTION AND ETHICAL OBLIGATIONS

13.1. Ethical and Regulatory Review

SOUTH AFRICA; CAPRISA/WITS Health Consortium: Ethical approval for the conduct of this study in South Africa will be sought from the UKZN Biomedical Research Ethics Committee (BREC) for ethical review for CAPRISA and the Human Research Ethics Committee (HREC) for WITS. Regulatory approval will be sought from South African Health Products Regulatory Authority (SAPHRA) for both clinical research sites in South Africa. These institutions are registered with the South African Department of Health's National Health Research Ethics Council (<http://www.doh.gov.za/nhrec>) (NHREC REC 200408-009), and the US Office for Human Research Protections (<http://www.hhs.gov/ohrp/>) (OHRP).

NIGERIA/IHVN: Ethical approval for the conduct of this study in Nigeria will be sought from the Nigerian National Health and Research Ethics Committee of Nigeria (NHREC), the IRB of the University of Maryland, Baltimore, (UMB) (the country PI is also a Professor of Medicine at UMB), and the health research ethics committees of all the participating clinics sites.

ETHIOPIA/EPHI: Ethical approval for the conduct of this study in Ethiopia will be sought from the Scientific and Ethical Review Office (SERO) which is the office of the secretariat for the institutional review board of Ethiopian Public Health Institute (EPHI). The protocol reviewed by EPHI-IRB will be submitted to National Research Ethics Review Committee (NRERC) as it involves human participants and new diagnostic that are not registered for use in Ethiopia.

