13.5. Good Clinical Practice

South Africa: The study will be carried out according to ICH-GCP and South African Good Clinical Practice Guidelines (SA GCP). The PI and/or designee will ensure that the study staff are conducting the study in accordance with current SA GCP and ICH-GCP guidelines, ensure appropriate human participants training for all study staff and safety of all study participants. The study protocol and participant informed consents and all future revisions of these latter documents will be reviewed and approved by UKZN BREC and SAPHRA prior to implementation. Quality control officers will perform daily quality checks on participant data and the Data manager will oversee the maintenance and completeness of the participant data.

All Serious Adverse Events (SAE's) will be reported to UKZN BREC and SAPHRA within 7 business days of site awareness. The DSMB will meet at designated timepoints to analyse and discuss safety data and make recommendations for the continuation of the study and participant care.

Nigeria: All study activities will be performed in accordance with the ICH-GCP guidelines and the NHREC code of conduct. Under the leadership of the Country PI, appropriate trainings on research ethics will be provided for the study team and clinic site personnel involved in the study implementation. Certificates from these trainings will be archived for reference purposes.

In line with the WHO recommendation for new medicines and regimens, active drug safety management and monitoring systems will be deployed to report SAE's and AE's of special interest. This will also be in accordance with the reporting guidelines of National Agency for Food and Drug Administration and Control (NAFDAC), as well as NHREC. To maintain high quality data capture, daily quality control checks will be performed on all filled case report forms.

Ethiopia: The study will be carried out according to ICH-GCP, Clinical Trial Authorization Guideline and National Research Ethics Review Guideline. The protocol will be approved by the national and institutional Ethics Committee. The Principal Investigator ensures the study is conducted as per the protocol. All study team will be trained on study participant enrolment, data management and security, safety of study participant.

Serious Adverse effect will be reported to the national clinical review committee and study team. The study team will ensure the recommendation is communicated and use for participant care.

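### Protocol 10.2 waives regulatory reporting for expected disease-related hospitalisations that 10.3 defines as SAEs and that 13.5 sends to the South African regulator within 7 business days

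*Protocol*

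**What the plan says.** Four parts of the protocol bear on which serious events leave the site and to whom.

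- **Section 10.2** lists expected disease-related events: death, HIV-related illness, antiretroviral side-effects and admission for respiratory or HIV-related reasons. It then says "Expected disease-related events will be recorded in study CRFs but will not require reporting to regulatory authorities", with the qualifier "unless the severity of the event was considered to be unexpected". The death entry carries its own clause, that it is reported as an SAE in every case. The antiretroviral entry reads "Common ART side-effects e.g. anaemia, sleep disturbance, diarrhoea, mild renal dysfunction".
- **Section 10.3** defines an SAE by the usual criteria, among them death and hospitalisation. Its one reporting sentence is "All serious ADRs will be reported". It names no recipient and no time limit.
- **Section 13.5**, South Africa, says "All Serious Adverse Events (SAE's) will be reported to UKZN BREC and SAPHRA within 7 business days of site awareness". No exception is stated.
- **Table 9** in section 10.4 gives, for linezolid, "Serious: myelosuppression (decreased level of platelets, white blood cells, and/or anaemia", and lists diarrhoea among the common reactions.

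Two smaller places touch the same process. Under section 8.1, an investigator who thinks treatment must be modified is told that "he or she should inform the coordinating centre by submission of an SAE form". Section 13.1 names "the Human Research Ethics Committee (HREC) for WITS", but the South African reporting line in 13.5 does not mention that committee.

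**The concern.** A site that admits a participant with worsening respiratory symptoms finds two opposite instructions. Section 10.2 says the regulator need not be told unless the severity was unexpected. Section 13.5 says the regulator must be told within 7 business days. Section 10.3, whose title suggests it would settle the matter, speaks only of serious adverse drug reactions.

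Section 13.4 makes each site solely responsible for its own regulatory submissions, adverse events included, so nothing in the protocol ensures that sites resolve the conflict in the same way. Section 10.2 itself says that such events may be frequent. Expedited reporting protects participants, and the safety of the all-oral regimens is a secondary objective.

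**Working it through.** No formula applies, and the protocol gives no event rates from which to count affected events. The check sets the sections against each other by type of event.

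**Admission for a respiratory or HIV-related reason**
- 10.3: an SAE, because it requires hospitalisation.
- 10.2: no report to regulatory authorities, unless severity is unexpected.
- 13.5, South Africa: report to UKZN BREC and SAPHRA within 7 business days.
- Result: direct contradiction. It concerns SAPHRA, which 13.1 identifies as the regulator for both South African sites. UKZN BREC is an ethics committee, so on its wording the 10.2 waiver does not reach the report to BREC.

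The qualifier in 10.2 does not remove the contradiction. It turns on severity, and section 10.1 states that severity and seriousness are different things. An admission of ordinary severity stays waived although it is serious by definition.

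**Death**
- 10.3: an SAE.
- 10.2: on the list to which the waiver applies, but with its own clause requiring that it be reported as an SAE.
- 13.5: reportable.
- Result: ambiguity within 10.2. The clause does not say whether the report goes to the regulator, so the closing sentence of 10.2 can be read either way.

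**Anaemia or diarrhoea in a participant on both antiretrovirals and linezolid**
- 10.2: expected, as an antiretroviral side-effect.
- Table 9: a linezolid reaction, with anaemia under the serious ones.
- 10.1: relatedness to study drug is assessed for every event, and the possible category includes events that another drug could explain.
- 10.3: if it is a serious adverse drug reaction, it is reported.
- Result: unclear attribution. Section 10.2 does not tie its waiver to the causality assessment in 10.1, so the protocol does not say which rule governs an event rated possible.

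**Extent**
- Section 6.2.1 allocates 440 of 880 cohort 1 participants to South Africa: 440 / 880 = 50%.
- The Nigerian paragraph of 13.5 provides for reporting SAEs and events of special interest under national guidelines. The Ethiopian paragraph sends serious events to a national review committee and the study team. Neither states an exemption, and neither has the explicit rule of all SAEs within 7 business days.

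**Recording, as distinct from reporting**
- The notes to Table 3 require all SAEs to be recorded throughout follow-up.
- Section 10.1 has all adverse events captured regardless of relationship, each with its seriousness.
- 10.2 keeps the expected events in the CRFs.
- Result: the waiver does not remove an event from the trial data. One small gap remains: 10.2 does not say that a waived admission is entered as an SAE.

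**The case against.** The strongest reply is that this is a narrow inconsistency of wording. The safety data are captured whichever section a site follows, the waiver concerns regulators and not the medical monitoring team or the DSMB, and no primary endpoint is touched. All of that stands, and it limits the point to expedited reporting.

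A reader might infer more, and the documents do not support it:

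- **That deaths are exempt.** The clause on death in 10.2 requires them to be reported as SAEs. What is left is uncertainty about the recipient.
- **That severe anaemia caused by linezolid goes unreported.** If judged a serious drug reaction, it is reportable under 10.3. The list in 10.2 attributes its anaemia to antiretrovirals. Only the attribution in participants on both is unclear.
- **That the SAE proportions in 9.2 are distorted by site or HIV status.** Those proportions come from study data, which include these events, and not from submissions to regulators.
- **That 8.1 inflates the SAE count.** It uses the SAE form as a route to notify the coordinating centre. It does not redefine an SAE, and nothing says that each such form is counted as one. The choice of form is awkward and no more.

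The missing ethics committee in 13.5 is editorial, since 13.4 already makes each site responsible for its own approvals and adverse event submissions.

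None of this removes the contradiction over respiratory and HIV-related admissions.

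**Conclusion.** The point holds in this form: an expected disease-related admission is an SAE under 10.3, is waived from regulatory reporting by 10.2 unless unexpectedly severe, and must reach the South African regulator within 7 business days under 13.5. Whether the waiver reaches death is ambiguous. Attribution of anaemia and diarrhoea is unclear in participants taking both antiretrovirals and linezolid.

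The explicit conflict applies to the South African half of cohort 1. The number of events affected cannot be given, because the protocol states no rates of admission or death. The conclusion rests on the wording alone and needs no assumption about event frequency. The consequence is inconsistent expedited reporting between sites, not loss of SAEs from the analysis.

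**What to change.** Reconcile 10.2, 10.3 and 13.5 into one reporting rule that names the recipient and time limit for each class of event, and state in 10.2 that the waiver does not apply to:

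1. death, or any other event meeting a 10.3 seriousness criterion, where 13.5 requires all SAEs to be reported;
2. any event judged possibly or probably related to a study drug.

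Two minor corrections belong in the same amendment. In 8.1, separate the notification of a treatment change from the SAE form, and keep that form for events that meet 10.3. In 13.5, add the HREC named in 13.1 to the reporting line for the WITS site.

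The cost is protocol wording and one instruction on form completion. The downside is a few more reports to regulators. No treatment rule, endpoint or sample size changes.

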10.3. Serious Adverse Event Reporting

An SAE or Serious Adverse Reaction (SAR) or Suspected Unexpected Serious Adverse Reaction (SUSAR) includes an experience where any AE, AR or UAR that at any dose:

- Results in death;
- Is life-threatening;
- Requires hospitalization or prolongation of existing hospitalization;
- Results in persistent or significant disability or incapacity; or is a medically significant/important event or reaction that may not be immediately life-threatening or result in death or hospitalization but may jeopardize the participant or may require intervention to prevent one of the other outcomes listed in the definition above.

All serious ADRs will be reported.

Special Circumstances	
Use in renal disease: No dosage adjustment is required in participants with mild to moderate renal impairment (dosing not established in severe renal impairment, use with caution).
 
Use in hepatic disease: No dosage adjustment is required in participants with mild to moderate hepatic impairment. Dosing and toxicity not well established in severe hepatic impairment, use with caution and only when the benefits outweigh the risks.
 
Use in pregnancy/breast feeding: Very limited data. Each case must be individually assessed.

Adverse Reactions*	
Common: Nausea, vomiting, abdominal pain, loss of appetite, joint pain (arthralgia), headache, chest pain, haemoptysis
 
Serious: QT prolongation (more common in hypokalaemia, proarrhythmic conditions, or if combined with other QTc-prolonging drugs), hyperuricaemia, phospholipidosis (the accumulation of phospholipids in the body's tissues), elevated aminotransferases. Possibly an increased risk of pancreatitis.

Contraindications	
Do not use or discontinue bedaquiline if:
 
 • Clinically significant ventricular arrhythmia. • A QTcF interval of >500ms (confirmed by repeat ECG). • Severe liver disease. 
Use with caution in the following situations (with more frequent ECG monitoring and evaluation of risk versus benefit):
 
 • Use with other QT prolonging drugs (see drug interactions) • A history of torsade de pointes • A history of congenital long QT syndrome • A history of hypothyroidism and bradyarrhythmias • A history of uncompensated heart failure

	
 • Serum calcium, magnesium or potassium levels below the lower limits of normal. 
Any syncopal event (e.g. fainting) should prompt immediate medical evaluation and ECG.

Drug Interactions*	
Anti-arrhythmic drugs, tricyclic anti-depressants, anti-psychotics, chloroquine & hydroxychloroquine, some other TB drugs (e.g. clofazimine & fluoroquinolones), and macrolide antibiotics may increase risk of QTc prolongation.
 
CYP3A4 inducers (including rifampicin, rifabutin, rifapentine, phenytoin and carbamazepine) can accelerate metabolism of bedaquiline resulting in reduced effect.
 
CYP3A4 inhibitors (including azole antifungals) slow metabolism of bedaquiline resulting in increased concentrations of bedaquiline.
 
Some anti-retroviral drugs are CYP3A4 inducers (e.g. efavirenz) or inhibitors (e.g. the protease inhibitors), so combined HIV and TB therapy requires careful consideration.

Guidance on monitoring	
ECG: before initiation of treatment, and at least 2, 4, 8, 12 and 24 weeks after starting treatment. More frequently if heart conditions, hypothyroidism or electrolyte disturbances are present.
 
LFT: at baseline and repeated monthly.

Pretomanid	
Activity against TB	Indicated as part of a combination regimen with bedaquiline and linezolid for treatment of adults with pulmonary XDR or treatment-intolerant or nonresponsive MDR TB
Dose	Pretomanid 200 mg daily 26 weeks
Special Circumstances	
Use in renal or hepatic disease: Effect on the safety, effectiveness, and pharmacokinetics unknown.
 
If hepatotoxicity develops on a pretomanid-containing regimen, the entire regimen should be interrupted if:
 
 • Any aminotransferase elevation is accompanied by a total bilirubin elevation $>2x$ ULN • Aminotransferase elevations are $>8 \times$ ULN • Aminotransferase elevations are $>5x$ ULN and persist beyond 2 weeks 
Any concerns about hepatotoxicity should be discussed promptly with the Medical Monitoring team.
 
There are no data on the use of pretomanid in pregnancy, or during breast feeding.

Adverse Reactions*	
In clinical trials of the bedaquiline-pretomanid-linezolid regimen, reported severe adverse reactions have included:
 
 • hepatotoxicity • myelosuppression, peripheral and optic neuropathy (all known adverse reactions to linezolid)

	
 QTc prolongation (known adverse reaction to bedaquiline) 
Pre-clinical animal studies reported testicular atrophy and fertility problems. Potential effects on human male fertility are still being evaluated.

Contraindications	
Pretomanid should always be initiated as part of a treatment regimen including bedaquiline and linezolid, so it is contraindicated if these drugs are contra-indicated.
 
After treatment initiation: If bedaquiline is discontinued, pretomanid must also be discontinued, and the entire regimen should be re-assessed.
 
If linezolid is permanently discontinued during the initial four consecutive weeks of treatment, the bedaquiline-pretomanid-linezolid regimen should also be discontinued and the entire treatment regimen should be re-assessed.
 
If linezolid is discontinued after the initial four weeks of consecutive treatment, the bedaquiline-pretomanid regimen may be continued.

Drug Interactions*	
CYP3A4 Inducers: Co-administration of pretomanid with rifampicin and efavirenz may result in a decrease in pretomanid plasma concentrations. Avoid co-administration of the combination bedaquiline-pretomanid-linezolid regimen with rifampin, efavirenz, or other strong or moderate CYP3A4 inducers.
 
Lopinavir/ritonavir (LPV/r): Co-administration of pretomanid with LPV/r did not affect the plasma concentrations of pretomanid. LPV/r can be co-administered with the combination bedaquiline-pretomanid-linezolid regimen.

Guidance on monitoring	
ECG before initiation of treatment.
 
Check serum potassium, calcium and magnesium and correct abnormalities before initiation of treatment.
 
Assess for symptoms and signs of liver disease (such as fatigue, anorexia, nausea, jaundice, dark urine, liver tenderness, and hepatomegaly and check LFTs (alanine aminotransferase [ALT], aspartate aminotransferase [AST], alkaline phosphatase, and bilirubin) before initiation of treatment.
 
Monitor clinically and biochemically for hepatotoxicity during treatment.

Linezolid	
Activity against TB, Mechanism of action, and metabolism	Bactericidal: Inhibits protein synthesis.

Dose	Adults: 600 mg, once daily. (Reduce to 300 mg/day if serious adverse effects develop). Ongoing trials may inform on revised dosing. Vitamin B6: All participants should receive vitamin B6 while receiving linezolid.
Special Circumstances	Use in renal disease: No dose adjustment is recommended, but metabolites may accumulate. Use in hepatic disease: Rarely associated with increased transaminases. Use in pregnancy/breastfeeding: Not recommended during pregnancy or breastfeeding due to limited data.
Adverse Reactions*	Common: diarrhoea, nausea, vomiting, headache, transient increases in LFTs. Serious: myelosuppression (decreased level of platelets, white blood cells, and/or anaemia), optic and peripheral neuropathy (increased risk with prolonged treatment and may be irreversible) lactic acidosis (may present recurrent nausea or vomiting, unexplained acidosis, or a low bicarbonate level).
Contraindications	Hypersensitivity to oxazolidinones. Symptoms of neuropathy (pain, numbness, tingling or weakness in the extremities).
Drug Interactions*	Avoid concurrent use with serotonergic agents, such as monoamine oxidase inhibitors (MAOIs), selective serotonin reuptake inhibitors (e.g. fluoxetine, paroxetine), lithium, tricyclic antidepressants etc., as it may cause serious neurological reactions such as seizures and serotonin syndrome.
Guidance on monitoring	Monitor for peripheral neuropathy and optic neuritis (visual eye tests every two months or if symptoms develop, clinical examination for peripheral neuropathy monthly or if symptoms develop). Monitor a complete blood count weekly during the initial period, then monthly.
Moxifloxacin	
Activity against TB, Mechanism of action, and metabolism	Bactericidal: inhibits DNA gyrase
Dose	Adults: 400 mg daily (oral or IV)
Special Circumstances	Use in renal disease: Excretion unchanged during renal failure; no data on effect of dialysis. Use in hepatic disease: Rarely associated with hepatotoxicity; use with caution. No dose adjustment required for mild or moderate liver disease. Use during pregnancy/breastfeeding: Fluoroquinolones are generally avoided during pregnancy and breastfeeding due to observation of arthropathy in animal models. However, there are

	case reports of fluoroquinolones being used safely during pregnancy.
Adverse Reactions*	Common: Nausea, vomiting, diarrhoea, dizziness, headache, transient increases in LFTs. Serious: QTc prolongation (more common in hypokalaemia, predisposing cardiac conditions, or if combined with other QTc prolonging drugs), arthralgia, tendon inflammation and/or rupture, hepatotoxicity, hypo/hyperglycaemia.
Contraindications	Fluoroquinolone intolerance, prolonged QTc (>500ms). Fluoroquinolones may lower seizure threshold, so use with caution in participants with CNS disorders.
Drug Interactions*	Caution if used alongside other drugs known to prolong QTc.
Guidance on monitoring	Symptomatic monitoring. Some guidelines recommend ECG at baseline, 2 weeks and every 3 months thereafter, especially if concurrent use with other medicines which may prolong QTc.
Levofloxacin	
Activity against TB, Mechanism of action, and metabolism	Bactericidal: inhibits DNA gyrase
Dose	Adults: For treatment of TB disease 10–15 mg/kg once daily. Renal failure/dialysis: 750–1000 mg/dose, 3 times weekly (not daily) for creatinine clearance <30 ml/min.
Special Circumstances	Use in renal disease: Dosage adjustment is recommended if creatinine clearance is <50 ml/min. The drug is not cleared by haemodialysis; supplemental doses after dialysis are not necessary. Use in hepatic disease: Drug concentrations are not affected by hepatic disease. Presumed to be safe in severe liver disease. Use during pregnancy/breastfeeding: Fluoroquinolones are generally avoided during pregnancy and breastfeeding due to observation of arthropathy in animal models. However, there are case reports of fluoroquinolones being used safely during pregnancy.
Adverse Reactions*	Nausea and bloating. Headache, dizziness, insomnia or tremulousness. Rare-tendon rupture, arthralgias (can usually be treated symptomatically). QTc prolongation, hypoglycaemia.
Contraindications	Fluoroquinolone intolerance, prolonged QTc (>500ms). Fluoroquinolones may lower seizure threshold, so use with caution in participants with CNS disorders.
Drug Interactions*	Caution if used alongside other drugs known to prolong QTc.
Guidance on monitoring	Symptomatic monitoring. Some guidelines recommend ECG at baseline, 2 weeks and every 3 months thereafter, especially if concurrent use with other medicines which may prolong QTc.

* Information on adverse reactions and drug interactions is not exhaustive. Please refer to pharmacy formulary, or discuss with the medical monitoring team as necessary.

